8.2.1.2. Drug-Related Adverse Events

Drug-related summary tables will be produced for AEs related to blinded study medication (albiglutide/placebo) only. No summaries will be produced for AEs related to insulin. This definition applies throughout the AE section, when drug-related events are mentioned. See Section 11.5.3 for further details.

If a relationship to the study drug is missing or unknown after the start of treatment it will be assumed, for the purpose of analyses, to be drug-related (to blinded study medication).

8.2.1.3. Adverse Events by Maximum Intensity

Subjects who experience the same event several times, with different intensity, will only be counted once according to the maximum intensity experienced (for that therapeutic phase). AEs with missing intensity will be considered to be severe for the purposes of summarisation.

8.2.1.4. Most Common Adverse Events

A summary of most common on-therapy adverse events ($\geq 6\%$ in any treatment arm) by treatment will be produced, presented by PT only (no SOC).

In addition, a summary of most-common on-therapy non-serious AEs (with $\geq 5\%$ incidence in any of the treatment groups) will be summarised by treatment group following government clinical register format. As specified in GSK's IDSL Adverse Event Statistical Display Standards document.

8.2.1.5. Deaths and Serious Adverse Events

Serious adverse events (SAEs) will be summarised. SAE data will be categorized and presented in a manner similar to that described for the general AE summaries (except presented by PT only, no SOC) by treatment group for pre-therapy, on-therapy, and post-therapy phases.

A summary of the number and percentage of subjects and the number of occurrences of serious, drug-related serious, fatal serious, and drug-related fatal serious adverse events will be created for disclosure requirements to regulatory agencies. The events will be grouped by SOC and PT in a similar manner to that described above for general AE summaries. The summary will be presented for the on-therapy phase.

Data listings will be presented for fatal SAEs and non-fatal SAEs. Due to the low number of SAEs reported in this study, summary tables for other SAE categories (e.g., drug related SAEs, fatal SAEs) will not be produced. The data listings will be used to identify these events.

8.2.1.6. Adverse Events Leading to Permanent Discontinuation of Investigational Product and/or Withdrawal from the Study

The overview of AEs will show the number of subjects with AEs leading to permanent discontinuation of study treatment and/or withdrawal from the study. However individual summary tables by SOC and PT will be produced for AEs leading to permanent discontinuation of study treatment (on-therapy phase), and AEs leading to withdrawal from the study (on-therapy and post-therapy phase separately).

8.2.1.7. Adverse Events of Special Interest

An overview summary of the number and percentage of subjects and the total number of AEs will be presented for: any AE of special interest (AESI); any serious AESI; any drug-related AESI; and any AESI leading to discontinuation of study treatment. The corresponding AE density will be presented for each on-therapy AESI. This summary will present results for each AESI by treatment group.

For any AEs of special interest, if the number of events is limited and does not warrant a summary table, then only by subject data listings will be provided.

AESI summary tables will present on-therapy AEs; AESI listings will present data from all therapy phases, and will include a flag to identify the therapy phase.

By-subject data listings will be provided for all AESI's, with the exception of Gastrointestinal Events (where information can be found within the main adverse event listing). The sections below indicate where AESI's have additional information collected on other eCRF pages, which will also be listed.

8.2.1.7.1. Cardiovascular Events

Investigators will be required to fill out event specific data collection tools for the following AEs and SAEs:

- Myocardial infarction/unstable angina
- Congestive heart failure
- Arrhythmias including atrial fibrillation/flutter
- Valvulopathy
- Pulmonary hypertension
- Cerebrovascular events/stroke and transient ischemic attack
- Peripheral arterial thromboembolism
- Deep venous thrombosis/pulmonary embolism
- Revascularisation

Cardiovascular events are reported by the Investigator on specific eCRFs for each event. These events are not adjudicated.

8.2.1.7.2. *Atrial Fibrillation/Atrial Flutter*

In addition to being included within the cardiovascular event ‘arrhythmias’ above, atrial fibrillation/atrial flutter events are also reported by the Investigator on a specific atrial fibrillation/atrial flutter eCRF.

8.2.1.7.3. *Subject-Reported Hypoglycaemic Events*

Subject-reported hypoglycaemia summaries include on-therapy and post-therapy events.

Hypoglycaemic events are reported in a subject eDiary; any meeting the SAE criteria are also reported in the adverse event data. The following summaries use subject-reported data (see Section 11.5.3). Incidence will be reported using the number and percentage of subjects experiencing events and the number of events.

Incidence of hypoglycaemia (in total and by each category as defined by ADA criteria) overall and in 3 monthly intervals will be summarised by treatment group.

Incidence of daytime hypoglycaemia (in total and by ADA category) and nocturnal hypoglycaemia (in total and by ADA category) will be summarised by treatment.

Incidence of hypoglycaemia with plasma glucose <3.1 mmol/L (< 56mg/dL), regardless of symptoms, will be summarised by treatment.

The number and percentage of subjects reporting hypoglycaemia during each two week period will be presented by treatment group. A summary table and plot will be produced. In addition, the number of hypoglycaemic events reported per subject during each two week period will be presented by treatment group. A summary table will be produced, and the mean number of hypoglycaemic events reported per subject during each two week period will be plotted.

Further exploratory analysis may be done, depending on the amount of missing data.

A by-subject listing of all subject-reported hypoglycaemic events will be produced.

Note: subject-reported hypoglycaemic events are also summarised as part of the secondary efficacy endpoints.

8.2.1.7.4. *Pneumonia*

Pneumonia events are reported by the Investigator on a specific pneumonia eCRF.

8.2.1.7.5. *Pancreatitis (Investigator-reported/Adjudicated)*

A by-subject listing of all the data elements collected on the pancreatitis eCRF pages will be presented for subjects who experienced pancreatitis (including the pancreatitis, abdominal ultrasound, abdominal CT scan, MRI and additional information forms). This listing of the pancreatitis events will also include the adjudication results as determined by the independent pancreatitis adjudication committee (PAC).

8.2.1.7.6. *Thyroid Adverse Events*

Thyroid adverse events are reported by the Investigator on a specific thyroid cancer, nodule or goiter diagnosis eCRF.

8.2.1.7.7. *Gastrointestinal (GI) Events*

A summary of the number and percentage of subjects with GI events (specifically, AEs coded to the MedDRA SOC of gastrointestinal disorders) will be reported by treatment group.

The number and percentage of subjects reporting any GI event at each study week will be presented by treatment group. Each week will include those subjects with onset of a GI event during that particular week and also those subjects with a GI event that started during a previous week but has not resolved.

Various characteristics of nausea, vomiting and diarrhoea will be summarised, separately.

8.2.1.7.8. *Injection Site Reactions*

Investigational product injection site reactions are reported by the Investigator on a specific injection site reaction eCRF.

Various characteristics of injection site reactions (like intensity, duration, size, outcome, action taken, onset relative time to the first and preceding dose, relationship to IP, number of events and symptoms) at the event level and subject level will be summarised. The number and percentage of subjects categorized by total number of injection site reactions (1, 2, 3 to 5, 6 to 10, 11 to 20, or >20 events) will also be provided.

A summary table of characteristics of injection site reactions will also be presented by anti-albiglutide antibody status. Subjects will be defined as positive or negative for anti-albiglutide antibody status. Anti-albiglutide positive subjects are defined as subjects with an anti-albiglutide antibody result of positive at any visit (including those with a positive

result at baseline, regardless of whether they had a post-baseline positive result). Anti-albiglutide negative subjects are defined as those subjects with an anti-albiglutide antibody result of negative at all visits.

8.2.1.7.9. *Systemic Allergic Reactions*

Potential systemic allergic reactions are reported by the investigators on the hypersensitivity eCRF.

For subjects with an investigator reported systemic allergic reaction, hypersensitivity medical history will be listed, along with additional hypersensitivity data collected following a systemic allergic reaction.

8.2.1.7.10. *Liver Events*

By-subject listings of all the data elements collected on the eCRF liver event pages will be presented for subjects who experience adverse liver events, as defined per protocol. This includes data recorded in the following eCRF forms: liver monitoring/stopping event recorded; liver events; alcohol intake at onset of liver event; medical conditions at onset of liver event; liver biopsy; liver imaging; and liver PK.

A summary table of Liver Monitoring/Stopping Event Reporting will also be presented using data from the liver events eCRF. This summary table will include events in both the on-therapy and post-therapy phases.

Additionally, a table summarising liver events identified by a Customised MedDRA Query (CMQ) will be presented for the on-therapy phase.

See Section [8.2.2](#) for additional related summaries based on laboratory data.

8.2.1.7.11. *Renal Impairment*

Renal impairment is reported by the investigators on the renal impairment eCRFs. By-subject listings of all the data elements collected on the eCRF renal impairment pages will be presented for subjects who experience renal impairment. This includes data recorded in the following eCRF forms: renal impairment; spot urine sample; timed urine sample; and additional information.

8.2.1.7.12. *Diabetic ketoacidosis (DKA)*

Diabetic ketoacidosis (DKA) events will be identified by a Customized MedDRA Query (CMQ).

8.2.1.7.13. *Appendicitis*

Appendicitis events will be identified by a Customized MedDRA Query (CMQ).

8.2.1.7.14. *Pancreatic Cancer*

Pancreatic cancer events will be identified by a Customized MedDRA Query (CMQ).

8.2.1.7.15. *Malignant Neoplasms*

Malignant neoplasms will be identified by a Standard MedDRA Query (SMQ).

8.2.2. Overview of Planned Clinical Laboratory Analyses

The safety analyses will be based on the “Safety” population, unless otherwise specified.

Table 7 provides an overview of the planned analyses, with further details of data displays being presented in [Appendix 13: List of Data Displays](#).

Table 7 Overview of Planned Clinical Laboratory Analyses

Endpoint / Parameter/ Display Type	Absolute			Change from BL		
	Summary		Individual	Summary		Individual
	T	F	L	T	F	L
Chemistry						
Chemistry Changes from Baseline				Y		
Chemistry Results by PCI Criteria	Y					
Hematology						
Hematology Changes from Baseline				Y		
Hematology Results by PCI Criteria	Y					
Urinalysis						
Urine Concentration Changes from Baseline				Y		
Summary of Urinalysis Dipstick Results	Y					
Hepatobiliary (Liver)						
Hepatobiliary Laboratory Abnormalities	Y					
Subjects Meeting Hepatobiliary Laboratory Criteria			Y			
Scatter Plot of Maximum vs. Baseline for ALT		Y				
Scatter Plot of Maximum Total Bilirubin vs Maximum ALT		Y				
All Laboratory						
All Laboratory Data for Subjects with any Value of PCI			Y			
Laboratory Data with Character Results			Y			

NOTES:

- T = Table, F = Figures, L = Listings, Y = Yes display generated, PCI = Potential Clinical Importance
- Summary = Represents TFL related to any summaries (i.e. descriptive statistics) of the observed raw data.
- Individual = Represents FL related to any displays of individual subject observed raw data.

8.2.2.1. Chemistry, Hematology and Urinalysis

Established or generally acknowledged methods, normal ranges, and quality control procedures will be supplied by Q2 Solutions for the study records.

Only data from the central laboratory will be included in the tables, figures and listings. Data from local laboratories will not be included.

Glucose data from the eDiary card will not be included in any laboratory TFLs.

The number of subjects with results relative to the potential clinical importance criteria will be summarised by laboratory test and category (including liver function tests). Data will be summarised by visit, including ‘any on-therapy visit’ and ‘any post-baseline visit’. The criteria for laboratory values of potential clinical importance are detailed in Section 11.7.1.

Urinalysis data with categorical results will be summarised at each assessed timepoint by treatment group, using number and percentage of subjects with each category.

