6.4. Safety

6.4.1. Safety Endpoints

- Hypoglycaemic Events
 - Incidence of hypoglycaemia (in total and by each category as defined by ADA criteria (see Section 6.4.2) overall and in 3 monthly intervals (i.e., from Baseline to Week 12, >Week 12 to ≤Week 24, >Week 24 to ≤Week 36, >Week 36 to ≤Week 52, >Week 52 to ≤Week 64
 - Incidence of hypoglycaemia with plasma glucose <3.1 mmol/L (< 56mg/dL) regardless of symptoms).
 - Incidence of daytime hypoglycaemia (in total and by category) (defined as hypoglycaemic episodes with an onset between 06:00 h and 00:00 h (inclusive) and nocturnal hypoglycaemia (in total and by category) defined as hypoglycaemic episodes with an onset between 00:01 h and 05:59 h (inclusive) will be determined.
 - Incidence of, and number of, hypoglycaemia with plasma glucose <3.9 mmol/l (< 70 mg/dL) regardless of symptoms) and/or requiring 3rd party assistance (i.e., severe, documented symptomatic and asymptomatic hypoglycaemic events) occurring > Week 24 and ≤ Week 52 (This is a secondary efficacy endpoint).
- Adverse events and serious adverse events
- Other adverse events of special interest (AESI) (for example, cardiovascular, gastrointestinal, pancreatitis, malignancies (including pancreatic cancer and thyroid cancer), injection site reaction, liver events, potential systemic allergic reactions,

atrial fibrillation/flutter, pneumonia, DKA [i.e., ketonuria/ketonaemia, hyperglycaemia and acidaemia])

- Assessment of clinical laboratory tests (haematology, biochemistry, urinalysis)
- Assessment of vital signs measurements, 12-lead ECGs and physical examinations
- Immunogenicity (e.g., percentage of subjects developing anti-albiglutide antibodies and characterisation of anti-albiglutide antibodies)

The following sections provide further detail on the safety assessments. Planned timepoints for all safety assessments are listed in the Time and Events Table ([Table 3](#)). Unscheduled visits will occur as medically necessary.

Liver chemistry stopping and follow-up criteria and AEs are described in [Section 6.4.9](#) and [Section 6.4.10](#) respectively.

For some AESI, specific eCRF pages will be used to capture additional details about the events (e.g., cardiovascular including atrial fibrillation/flutter ([Section 6.4.12](#)), injection site reactions, pancreatitis, thyroid cancer, pneumonia).

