6.4.7. Clinical Laboratory Assessments

All protocol required laboratory assessments, as defined in Table 3, must be performed by the central laboratory, Quest Diagnostics Clinical Laboratory. Note: Screening T1DM auto-antibody tests may be carried out at local labs if results are required quickly, however a sample is to be sent to the central lab as well. Laboratory assessments must be conducted in accordance with the Central Laboratory Manual and Protocol Time and Events Schedule. Laboratory requisition forms must be completed and samples must be clearly labelled with the subject number, protocol number, site/centre number, and visit date. Details for the preparation and shipment of samples will be provided by Quest Diagnostics Clinical Laboratory. Reference ranges for all safety parameters will be provided to the site by Quest Diagnostics Clinical Laboratory.

If additional non-protocol specified laboratory assessments are performed at the institution's local laboratory and result in a change in patient management or are considered clinically significant by the investigator (e.g., SAE or AE or dose modification), the results must be recorded in the subject's CRF. Refer to the SPM for appropriate processing and handling of samples to avoid duplicate and/or additional blood draws.

Haematology, clinical chemistry, urinalysis, and other laboratory assessments are detailed below and will be collected at time points specified in the Time and Events Table ([Table 3](#)).

During visits when ECGs and vital signs are scheduled, blood samples will be collected after the completion of these assessments.

Haematology:

- Complete blood count with haemoglobin and other red blood cell indices, white blood cell count differential, and platelet count

Clinical Chemistry:

- Glucose, blood urea nitrogen, creatinine, sodium, potassium, chloride, carbon dioxide, calcium, total protein, albumin, total bilirubin, direct bilirubin, alkaline phosphatase, ALT, AST, γ -glutamyltransferase, uric acid, magnesium, and phosphorus

Urinalysis:

- Specific gravity, pH, glucose, protein, blood by dipstick (if warranted, a microscopic evaluation will be completed)

Other urine tests at time points specified in the Time and Events Table:

- Urine pregnancy test (β human chorionic gonadotropin [β -HCG]) for female subjects of child bearing potential
- Urinary C-peptide and urinary creatinine as part of the MMTT (see [Section 6.3.2.1](#))

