6.4.9. Liver chemistry stopping and follow up criteria

Liver chemistry stopping and follow up criteria have been designed to assure subject safety and evaluate liver event etiology (in alignment with the FDA premarketing clinical liver safety guidance).

liver chemistry stopping criteria 1-5 are defined below and are presented in a figure in Appendix 2 :

1. ALT \geq 3xULN and bilirubin \geq 2xULN (>35% direct bilirubin) (or ALT \geq 3xULN and INR>1.5, if INR measured)

NOTE: if serum bilirubin fractionation is not immediately available, withdraw study drug for that subject if ALT \geq 3xULN and bilirubin \geq 2xULN. Serum bilirubin fractionation should be performed if testing is available. If testing is unavailable, **record presence of detectable urinary bilirubin on dipstick**, indicating direct bilirubin elevations and suggesting liver injury.

2. ALT \geq 8xULN.
3. ALT \geq 5xULN but <8 xULN persists for \geq 2 weeks

4. ALT \geq 3xULN if associated with symptoms (new or worsening) believed to be related to hepatitis (such as fatigue, nausea, vomiting, right upper quadrant pain or tenderness, or jaundice) or hypersensitivity (such as fever, rash or eosinophilia).
5. ALT \geq 5xULN but $<$ 8 xULN and cannot be monitored weekly for \geq 2 weeks

When any of the liver chemistry stopping criteria 1-5 is met, do the following:

- **Immediately** withdraw investigational product for that subject
- Report the event to GSK **within 24 hours** of learning its occurrence
- Complete the liver event CRF and SAE data collection tool if the event also meets the criteria for an SAE. All events of ALT \geq 3xULN **and** bilirubin \geq 2xULN ($>$ 35% direct) (or ALT \geq 3xULN **and** INR $>$ 1.5, if INR measured); INR measurement is not required and the threshold value stated will not apply to patients receiving anticoagulants), termed 'Hy's Law', **must be reported as an SAE (excluding studies of hepatic impairment or cirrhosis).**

NOTE: if serum bilirubin fractionation is not immediately available, withdraw study drug for that subject if ALT \geq 3xULN **and** bilirubin \geq 2xULN. Serum bilirubin fractionation should be performed if testing is available. If testing is unavailable, **record presence of detectable urinary bilirubin on dipstick**, indicating direct bilirubin elevations and suggesting liver injury.

- Complete the liver imaging and/or liver biopsy CRFs if these tests are performed

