
 Summaries of subject-reported events over time will calculate percentages based on the number of subjects at risk of an event within each time period. i.e., the Ns will be expected to decrease over time as subjects withdraw from the study The date of study withdrawal will be used as the end-date of the 'at-risk' period for each subject, as subject-reported hypoglycaemic events are reported throughout the study period i.e., until week 64 or study withdrawal. A subject will not be included as 'at-risk' in a particular period if their study withdrawal date is before the start date of the interval.
Hypoglycaemic Events with Glucose $<3.1\text{mmol/L}$

 Hypoglycaemic events with a plasma glucose $<3.1\text{ mmol/L}$ ($<56\text{ mg/dL}$) will also be identified.
Laboratory Parameters
Only data from the central laboratory will be included in the tables, figures and listings. Data from local laboratories will not be included.
eGFR

 $\text{eGFR} (\text{mL/min}/1.73\text{ m}^2) = 175 \times (\text{S}_{\text{cr}})^{-1.154} \times (\text{Age})^{-0.203} \times (0.742 \text{ if female}) \times (1.212 \text{ if African American})$ eGFR will be calculated based on measured creatinine and associated age. For this purpose, associated age (in whole years) will be calculated with respect to the date of creatinine sample using the imputed date of birth (see Section 11.6.2.1). This derived eGFR will be used for summary tables.
Glucose data not included in laboratory TFLs

 Glucose readings from the MMTT will not be included in any laboratory TFLs. These are identified in SDTM.LB as LBTEST='Glucose' and LBTPTNUM = 10, 20, 30, 40, 50, 60, 70. Finger-stick glucose readings for the MMTT will not be included in any laboratory TFLs. These can be identified in the SDTM.LB dataset using LBTEST='Glucose' and VISIT ne " and LBNAM='NOT APPLICABLE - NO RANGES EXPECTED', LBTPPT=' ' and LBSPEC='BLOOD'. Glucose data from the eDiary card and 72h CGM will not be included in any laboratory TFLs. The glucose data from the eDiary and 72h CGM can be identified in the laboratory domain/dataset (SDTM.LB) as LBTEST = "Glucose" and LBNAM="NOT APPLICABLE – NO RANGES EXPECTED". 
 Subject reported Hypoglycaemic event glucose readings are identified where LBTPT

Laboratory Parameters

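### The SAP keeps CRF-recorded local laboratory results out of all laboratory displays, and plans an ALT-plus-INR row for which no scheduled central INR exists

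*SAP*

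**What the plan says.** **The exclusion.** SAP 8.2.2.1 reads "Only data from the central laboratory will be included in the tables, figures and listings". The Laboratory Parameters part of SAP 11.5.3 repeats this and adds "Data from local laboratories will not be included". Both statements sit in laboratory sections.

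**What is collected.** Protocol 6.4.7 says "All protocol required laboratory assessments, as defined in Table 3, must be performed by the central laboratory". It then covers tests done outside the protocol at the site's own laboratory. If they "result in a change in patient management or are considered clinically significant by the investigator", the results must be entered in the CRF. Protocol 8.3.5.1 promises complete data listings.

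**The liver criteria.** Criterion 1 in Protocol 6.4.9 is raised ALT with raised bilirubin or, alternatively, raised ALT with "INR>1.5, if INR measured". The Hepatotoxicity part of SAP 11.5.3 plans to summarise both combinations, with the INR cut-off written as 1.5 times ULN. The displays concerned are Table 3.52, Listing 75 and the eDISH plot (Figure 3.4).

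**DKA.** Protocol 6.4.1 describes it as "DKA [i.e., ketonuria/ketonaemia, hyperglycaemia and acidaemia". SAP 8.2.1.7.12 identifies it by a MedDRA query on coded terms (Table 3.41, Listing 69).

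**The concern.** Keeping local values out of by-visit means is sound practice, because assay methods and reference ranges differ. Keeping them out of listings is another matter. The protocol selects these results because someone acted on them or judged them important, and the SAP gives them no laboratory display.

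The exclusion also sits badly with the SAP's own approach to extremes. SAP 11.4.3 admits unscheduled values to worst-case laboratory summaries and to the hepatobiliary figures, which picks up peaks between visits. If such a peak was measured locally, it is still left out.

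At stake is the reading of individual safety cases in the first albiglutide study in this indication (Protocol 1.3). An empty cell in a liver table tends to be read as reassurance, and here it may only reflect an absence of eligible data. The primary endpoint is not affected.

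**Working it through.** The plan gives no figure to reproduce, so the check sets the sections side by side.

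**1. What the scheduled central panels contain (Protocol 6.4.7).** Chemistry begins "Glucose, blood urea nitrogen, creatinine, sodium, potassium, chloride, carbon dioxide, calcium, total protein, albumin, total bilirubin, direct bilirubin, alkaline phosphatase, ALT, AST" and continues with γ-glutamyltransferase, uric acid, magnesium and phosphorus. Haematology is "Complete blood count with haemoglobin and other red blood cell indices, white blood cell count differential, and platelet count". Urinalysis covers specific gravity, pH, glucose, protein and blood.

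| Quantity | Where the plan relies on it | In the scheduled central panels? |
|---|---|---|
| ALT, total and direct bilirubin | Protocol 6.4.9; SAP 11.5.3 Hepatotoxicity | Yes |
| INR | Protocol 6.4.9; SAP 11.5.3 Hepatotoxicity | No; optional |
| Glucose | DKA description | Yes |
| Blood pH | DKA description (acidaemia) | No; the urinalysis pH is urine pH, and carbon dioxide is only an indirect marker |
| Ketones | DKA description | No; subjects test urine with Ketostix (Protocol 5.1.2) |

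**2. The INR row.** Protocol 6.4.9 and 6.4.10.2 make INR optional and send any measured value to the SAE form. The planned row therefore has no scheduled central source. A central INR is not ruled out: Protocol 6.4.9 names follow-up tests outside the scheduled panels and does not say which laboratory runs them.

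**3. ALT and bilirubin.** Both are measured centrally on schedule. The exclusion affects only a peak measured locally, between visits or at an acute presentation. That value would be missing from Table 3.52, Listing 75 and Figure 3.4. Nor could it bring a subject into Listing 73, which covers only subjects with a value of potential clinical importance.

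**4. Was the change declared?** SAP 2.1 says that departures from the protocol's planned analysis are set out in Table 1. That table covers values beyond quantification limits and repeated laboratory tests. It has no entry for local results.

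**5. The two INR thresholds.** The protocol cut-off is 1.5. The SAP cut-off is 1.5 × ULN. The documents give no ULN for INR, so a range is assumed:
- ULN 1.0: 1.5 × 1.0 = 1.50
- ULN 1.1: 1.5 × 1.1 = 1.65
- ULN 1.2: 1.5 × 1.2 = 1.80
- ULN 1.3: 1.5 × 1.3 = 1.95

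The two agree only if ULN is 1.0. At an assumed ULN of 1.3, an INR above 1.5 and up to 1.95 meets the protocol criterion but not the SAP row.

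**The case against.** The strongest reply is that the rule governs laboratory displays only, and serious cases reach the report by other routes.

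- Every case of raised ALT with raised bilirubin, or with raised INR where measured, must be reported as an SAE (Protocol 6.4.9, 6.4.10.2). It should then appear in the SAE tables and Listings 41 to 43.
- SAP 8.2.1.7.10 lists every data element on the liver event eCRF pages (Listings 58 to 63), and Table 3.51 summarises liver monitoring and stopping events.
- Protocol 6.4.11 requires clinically significant abnormalities to be reported as AEs or SAEs, apart from disease-related ones no more severe than expected.
- Subjects who meet a stopping criterion are recalled for repeat chemistries, which may well be central.
- Protocol 6.4.7 requires local results to be recorded, not displayed.

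Most of this stands. A reader might infer that a Hy's Law case could be lost, and weigh one case as 1/51 = 2.0% of the albiglutide arm or 1/17 = 5.9% of placebo. The documents do not support that, because the case should still be counted as an SAE. A reader might also infer that the INR row must be empty, but a central INR remains possible.

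Nor does the exclusion explain the lack of a laboratory check on DKA. The SAP defines DKA by coded terms and plans no laboratory confirmation, so lifting the rule would not by itself create one. Ketostix readings are not laboratory data, and glucose and carbon dioxide are central.

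The reply leaves three things unanswered. The documents do not say whether the liver pages hold INR. The event listings do not feed Table 3.52, Listing 75 or the eDISH plot. And the promise of complete listings was narrowed without being declared.

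**Conclusion.** The point holds as a gap in display and declaration, and it is cheap to close. Local results that the protocol requires in the CRF have no place in any laboratory table, figure or listing. The ALT-plus-INR row has no scheduled central source and no stated denominator, so a zero there cannot be interpreted. A local ALT or bilirubin peak would be absent from three hepatobiliary displays. The INR threshold differs between protocol and SAP unless ULN is 1.0.

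The size cannot be put as a percentage, because the documents do not say how many local results or INRs were recorded. The ALT-plus-bilirubin criterion remains checkable from central data, and the point does not extend to DKA or Hy's Law cases being missed or unverifiable.

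Two assumptions underlie this: that the exclusion is confined to laboratory displays, as its placement suggests, and that the test lists in Protocol 6.4.7 are the full scheduled central panel.

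**What to change.** Amend SAP 8.2.2.1 and 11.5.3 as follows:

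1. Keep by-visit summaries central-only.
2. Add a by-subject listing of all CRF-recorded local results, with the local reference range where recorded. Include any results around DKA events, so that they can be read beside Listing 69.
3. Let INR from any source count in Table 3.52 and Listing 75. Do the same for local ALT and bilirubin where a local ULN is available. Flag each such entry as local.
4. Show the number of subjects with at least one INR as the denominator of the INR row.
5. Reconcile the INR threshold in SAP 11.5.3 with Protocol 6.4.9 and 6.4.10.2.
6. Record the change in SAP Table 1.

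The cost is SAP wording, one extra listing, some programming for Table 3.52 and Listing 75, and mixed methods and reference ranges in the flagged entries. The documents do not say whether local ranges are captured. Where they are not, local ALT and bilirubin would be listed but not counted. No new data collection is needed.
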